9.6.1 Data Collection

Data required by the protocol will be collected on the eCRFs and entered into a validated data management system that is compliant with all regulatory requirements. As defined by ICH guidelines, the CRF is a printed, optical, or electronic document designed to record all of the protocol-required information to be reported to the sponsor on each study subject.

Data collection on the eCRF must follow the instructions described in the CRF Completion Guidelines. The investigator has ultimate responsibility for the collection and reporting of all clinical data entered on the eCRF. The investigator or designee as identified on Form FDA 1572 (where applicable) must sign the completed eCRF to attest to its accuracy, authenticity, and completeness.

Completed, original eCRFs are the sole property of Eisai and should not be made available in any form to third parties without written permission from Eisai, except for authorized representatives of Eisai or appropriate regulatory authorities.

9.6.2 Clinical Data Management

All software applications used in the collection of data will be properly validated following standard computer system validation that is compliant with all regulatory requirements. All data, both eCRF and external data (eg, laboratory data), will be entered into a clinical system.

Electronic source (eSource) methodology may be used for some of the clinical efficacy assessments performed in this study.

9.7 Statistical Methods

All statistical analyses will be performed by the sponsor or designee. Statistical analyses will be performed using SAS software or other validated statistical software as required.

All statistical tests will be based on the 5% (2-sided) level of significance. (revised per Amendment 05)

9.7.1 Statistical and Analytical Plans

The statistical analyses of Core Study data are described in the following sections. Statistical analyses of OLE Phase data are provided in [Appendix 6](#). (revised per Amendment 07)

Analyses will be performed based on treatment group, which will be defined in the statistical analysis plan (SAP). Additional analyses related to dose re-assignment will be performed for subjects who will be switched from elenbecestat (E2609) 5 or 15 mg to elenbecestat (E2609) 50 mg. Further details will be provided in the SAP, which will be finalized before database lock. (revised per Amendment 06)

9.7.1.1 Study Endpoints

9.7.1.1.1 PRIMARY ENDPOINT

- Safety and tolerability, which include incidence of TEAEs and SAEs, laboratory parameters, vital signs, and ECG parameters (revised per Amendment 05)

9.7.1.1.2 SECONDARY ENDPOINTS

(revised per Amendments 02 and 05)

- % reduction of A β (1-x) and A β (1-42) in CSF relative to baseline after from 4 weeks and up to 18 months of treatment

- The population PK parameters of elenbecestat (E2609) in CSF and plasma, including the effect of intrinsic and extrinsic factors (including NAT2 phenotype) (revised per Amendment 07)

9.7.1.1.3 EXPLORATORY ENDPOINTS

(revised per Amendments 01, 02, 04, and 05)

Change from baseline in:

- CSF A β (1-40) and BACE1 variables (eg, activity and protein levels) after at least 4 weeks and at 18 months of treatment
- CSF biomarkers of neurodegeneration (eg, t-tau and p-tau) at 18 months of treatment
- Plasma amyloid measurements from 4 weeks and up to 18 months of treatment, and during posttreatment follow-up
- CSF amyloid and CSF BACE1 measurements after 4 weeks and 18 months of treatment (revised per Amendment 06)
- Total hippocampal volume at 12 and 18 months of treatment as measured by vMRI
- Left and right hippocampal, whole brain, and total ventricular volume at 6, 12, and 18 months of treatment as measured by vMRI
- Amyloid PET standardized uptake value ratio (SUVR) composite at 18 months for brain amyloid levels as measured
- The following clinical assessments at 12 weeks and at 6, 9, 12, 15, 18, 19, and 21 months: ADAS-cog₁₄, CDR, MMSE, ISLT, CBB, and FAQ

9.7.1.2 Definitions of Analysis Sets

- The Randomized Set is the group of subjects who are randomized to study drug.
- The Safety Analysis Set is the group of subjects who receive at least 1 dose of study drug and have at least 1 postdose safety assessment.
- The Full Analysis Set (FAS) is the group of randomized subjects who receive at least 1 dose of study drug and have baseline and at least 1 postdose exploratory efficacy measurement. (revised per Amendment 05)
- The PK Analysis Set is the group of subjects with at least 1 quantifiable elenbecestat (E2609) plasma concentration accompanied by a documented dosing history. (revised per Amendment 07)
- The PD Analysis Set is the group of subjects who have a baseline PD measurement and at least 1 posttreatment PD measurement.

9.7.1.3 Subject Disposition

The number of subjects screened, the number (percent) of subjects who failed screening, and the reasons for screen failure will be summarized, based on data reported on the Screening Disposition eCRF. The number of randomized subjects enrolled at each site will be summarized by treatment group. The primary reasons for screen failures (did not meet inclusion or met exclusion criteria, AE, lost to follow-up, withdrawal of consent, and other) will be presented.

Study Completion: The number (percent) of randomized and treated subjects who completed the study and who withdrew from the study will be summarized according to the primary reason for discontinuation and secondary reason(s) for discontinuation, based on data reported on the Subject Disposition (Study Phase) CRF. The number (percent) will be presented by treatment group and total for subjects; randomized, not treated, treated, who completed the study, and withdrew from the study. The primary reasons for discontinuation from the study are: AE, lost to follow-up, subject choice, withdrawal of consent, pregnancy, study terminated by sponsor, and other. The secondary reasons for discontinuation from the study are: AE, subject choice, and other.

Completion of Study Treatment: The number (percent) of randomized and treated subjects who completed study drug and who discontinued from study drug will be summarized according to the primary reason for discontinuation and also according to secondary reason(s) for discontinuation, based on data reported on both the Subject Disposition (Study Phase) eCRF and ED from Study Drug eCRF. The number (percent) will be presented by treatment group and total for subjects; randomized, not treated, treated, who completed study drug, and discontinued from study drug. The primary reasons for discontinuation from the study drug are: AE, lost to follow-up, subject choice, withdrawal of consent, pregnancy, study terminated by sponsor, inadequate therapeutic response, and other. The secondary reasons for discontinuation from the study are: AE, subject choice, and other.

9.7.1.4 Demographic and Other Baseline Characteristics

Demographic and other baseline characteristics for the Safety Analysis Set and FAS will be summarized by treatment group using descriptive statistics. Continuous demographic and baseline variables include age, MMSE and FAQ; categorical variables include sex, age group (≤ 65 years, age > 65 years), race, ethnicity, *ApoE4* status (positive or negative), prior treatment with AChEIs or memantine (no or yes), and clinical population (MCI/Prodromal AD or mild to moderate AD). (revised per Amendment 01)

9.7.1.5 Prior and Concomitant Therapy

All investigator terms for medications recorded in the eCRF will be coded to an 11-digit code using the World Health Organization Drug Dictionary (WHO DD) (Mar 2014 or higher). (revised per Amendment 04) The number (percentage) of subjects who took prior and

concomitant medications will be summarized on the Safety Analysis Set by treatment group, Anatomical Therapeutic Chemical class, and WHO DD preferred term. Prior medications will be defined as medications that stopped before the first dose of study drug. Concomitant medications will be defined as medications that (1) started before the first dose of study drug and were continuing at the time of the first dose of study drug, or (2) started on or after the date of the first dose of study drug up to the date of the last dose. All medications will be presented in subject data listings.

Medications taken within the 12-week Follow-Up period will also be recorded.

9.7.1.6 Efficacy and Biomarker Analyses (revised per Amendment 05)

9.7.1.6.1 PRIMARY EFFICACY ANALYSIS

There is no primary efficacy endpoint. (revised per Amendment 05)

9.7.1.6.2 SECONDARY EFFICACY ANALYSES

An mixed-effects model with repeated measures (MMRM) will be used to analyze the following secondary endpoint:

- Change from baseline in CSF A β (1-x) and CSF A β (1-42) from 4 weeks and up to 18 months. Data from early discontinuations will also be included. (revised per Amendment 05)

9.7.1.6.3 EXPLORATORY EFFICACY ANALYSES

(revised per Amendments 01, 02, 04, and 05)

An MMRM will be used to analyze the following exploratory endpoints:

- Change from baseline in CSF A β (1-40) and BACE1 variables (eg, activity and protein levels) from 4 weeks and up to 18 months. Data from early discontinuations will also be included. (revised per Amendment 04)
- Change from baseline in CSF biomarkers of neurodegeneration (eg, t-tau and p-tau) at 18 months of treatment
- Change from baseline in plasma amyloid measurements from 4 weeks and up to 18 months of treatment, and during posttreatment follow-up
- Change from baseline in CSF amyloid and CSF BACE1 measurements from 4 weeks and up to 18 months of treatment (revised per Amendment 06)
- Change from baseline in total hippocampal atrophy at 12 and 18 months as measured by vMRI
- Change from baseline in left and right hippocampal, whole brain, and total ventricular volume at 6, 12 and 18 months as measured by vMRI

- Change from baseline in Amyloid PET SUVR composite at 18 months for brain amyloid levels

The following efficacy endpoints will be summarized using descriptive statistics:

- Change from baseline in the clinical assessments: ADAS-cog₁₄, CDR, MMSE, ISLT, CBB, and FAQ at 12 weeks and at 6, 9, 12, 15, 18, 19, and 21 months

The relationship between efficacy endpoints and biomarker endpoints will be explored using correlation analysis.

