8.3 Exploratory Objectives

(revised per Amendments 01,02, 04, and 05)

The exploratory objectives are:

To explore the effects of elenbecestat (E2609) compared on CSF A β (1-40) and BACE1 measurements from 4 weeks and up to 18 months of treatment

To explore the effects of elenbecestat (E2609) compared with placebo on various biomarkers. Biomarkers to be explored may include, but not limited to:

- a. CSF biomarkers of neurodegeneration (eg, total tau [t-tau], phosphorylated-tau [p-tau]) after 18 months of treatment
- b. Plasma and CSF amyloid, and CSF BACE1 measurements from 4 weeks and up to 18 months of treatment (revised per Amendment 06)
- c. Total hippocampal atrophy at 12 and 18 months of treatment, as measured by volumetric magnetic resonance imaging (vMRI)
- d. vMRI measurements including left and right hippocampal volume, whole brain volume, and total ventricular volume at 6, 12, and 18 months of treatment
- e. Brain amyloid levels at 18 months as measured by amyloid positron emission tomography (PET)

To explore the effects of elenbecestat (E2609) compared with placebo on clinical status at various time points during 18 months of treatment, and during posttreatment follow-up by assessment of:

-
- a. The Alzheimer's Disease Assessment Scale – cognitive subscale (ADAS-cog₁₄)
 - b. The Clinical Dementia Rating (CDR) scale
 - c. The Mini-Mental State Examination (MMSE)
 - d. The International Shopping List Task (ISLT)
 - e. The CogState Brief Battery (CBB)
 - f. The Functional Assessment Questionnaire (FAQ; (also known as the Functional Activities Questionnaire)

To explore the relationship between the treatment effects of elenbecestat (E2609) on measured clinical efficacy scales (eg, MMSE, CDR) and its effects on CSF amyloid, CSF amyloid isoforms, brain amyloid, and vMRI

To explore relationships between both elenbecestat (E2609) dose and exposure, with PD and safety endpoints

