9.2.4.3 Amyloid PET

Amyloid PET imaging will be used in this study for 2 primary reasons: 1) to confirm the presence of AD pathology in the brain of subjects with MCI/Prodromal AD or mild to moderate AD at entry to the study; and 2) to evaluate the effects of elenbecestat (E2609) on amyloid levels in the brain, both by whole brain analysis (the average of 5 to 6 cortical regions) and brain region analysis. (revised per Amendment 01)

Longitudinal amyloid PET imaging will be conducted after 18 months of treatment in the Core Study (or at ED, providing the subject has received at least 39 weeks of study drug) as an exploratory measure of the potential disease-modifying effects of elenbecestat (E2609). (revised per Amendment 07) Longitudinal amyloid PET imaging will only be conducted on subjects with Screening PET scans performed for this study (ie, historical scans cannot be used for the longitudinal analyses). (Revised per Amendments 02 and 05)

9.2.4.4 vMRI

Volumetric imaging will be used to evaluate the effects of elenbecestat (E2609) on rates of atrophy across the different dose groups during the Core Study and to provide support that effective treatment is associated with modification of disease course (exploratory endpoints in the Core Study and OLE Phase). (revised per Amendments 01 and 07) A large body of data has shown that structural MRI reliably tracks disease progression in AD. Atrophy tends to occur preferentially in the lateral temporal and posterior parietal regions during the early stages of disease and progresses towards the anterior regions of the brain (frontal cortex) in its later stages. Clinically efficacious doses are predicted to be associated with a slowing in the rate of hippocampal atrophy compared with rates observed in the placebo and non-efficacious dose groups. Treatment effects on left and right hippocampal, whole brain, and total ventricular volumes are exploratory endpoints.

Annualized rates of change of 2% to 3% have been reported for the AD brain compared with 1% in MCI and <1% in age-matched controls (Hua, et al., 2010, Leung, et al., 2010).

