- q: Safety MRIs will be acquired using a standardized procedure that will include gradient echo, long tau inversion recovery, and diffusion-weighted imaging sequence images in MRI will be read by an approved central reader. MRI imaging will be conducted on separate days from the scheduled visits. MRI imaging should be conducted within the 7 days before Visits 14, 16, 18, and 20. In the event of an Unscheduled Visit, the investigator in consultation with the sponsor will determine whether or not a safety MRI should be conducted. If an ED Visit takes place, an MRI is to be conducted if not already performed during the preceding 90 days. A volumetric MRI sequence will be collected in all subjects immediately following all safety MRI assessments. (revised per Amendment 01)
- r: PET scanning will be performed with a locally approved amyloid β imaging agent, eg, Amyvid, if available or an agent under clinical investigation if no agents are approved locally; the imaging agent must remain unchanged for an individual subject throughout the study. A PET scan will only be performed at an ED Visit if the subject has been treated with study drug for at least 39 weeks. A PET scan will only be performed at Visit 18 or ED if the subject has a valid Screening PET scan for the purposes of longitudinal analyses; subjects who were determined to be eligible for the study on the basis of an historical PET scan will not have a PET scan performed at Visit 18 or ED (revised per Amendment 02)
- s: Site staff will contact the subject or the caregiver or informant the day before the PK blood sampling to provide instructions that subjects must not take their study drug at home on the day of the PK blood sampling. During this telephone contact with the subject or the caregiver or informant, the site staff should document the time that the subject took their study drug that day, ie, the day before the PK blood sampling.

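### Total hippocampal volume is listed for analysis only at 12 and 18 months, although the same scans give left and right hippocampus a 6-month time point

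*Protocol*

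**What the plan says.** Total hippocampus carries the same two time points wherever the protocol lists it:

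- **Objective, section 8.3, item c:** atrophy at 12 and 18 months.
- **Endpoint, section 9.7.1.1.3:** "Total hippocampal volume at 12 and 18 months of treatment as measured by vMRI".
- **Analysis, section 9.7.1.6.3, by MMRM:** "Change from baseline in total hippocampal atrophy at 12 and 18 months as measured by vMRI".
- **Synopsis:** the same restriction (the full synopsis text shown is that of the Amendment 06 version).

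The adjacent MMRM item, for the other volumes, reads "Change from baseline in left and right hippocampal, whole brain, and total ventricular volume at 6, 12 and 18 months as measured by vMRI".

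On acquisition, footnote q to Table 7 says "MRI imaging should be conducted within the 7 days before Visits 14, 16, 18, and 20" and "A volumetric MRI sequence will be collected in all subjects immediately following all safety MRI assessments". In Table 7 these visits fall at 6, 12, 18 and 21 months, the last being 12 weeks after the final dose. The same footnote adds: "If an ED Visit takes place, an MRI is to be conducted if not already performed during the preceding 90 days".

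**The concern.** The 6-month hippocampal data exist in all subjects who reach Visit 14, and the protocol plans to model them side by side. Leaving them out only for the total is unexplained. Scan noise is an unlikely reason, because section 9.2.4.4 plans volumetric analysis every 6 months and describes structural imaging as reliable over such intervals.

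Three things follow.

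1. Left, right and total can rest on different subjects, because someone with only a 6-month scan counts for the sides and not for the total.
2. An MMRM handles dropout by using the earlier values that it holds. Without the first post-baseline value, the total model has less to draw on for early dropouts.
3. Amendment 06 moves 5 and 15 mg subjects who have not completed Visit 17 to 50 mg. Section 9.2.4.4 predicts slower hippocampal atrophy at efficacious doses than on placebo and at non-efficacious doses. For some switched subjects, the 6-month scan is the only scheduled treatment-period scan that bears on that prediction at their randomised dose.

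The wording also slips: the endpoint is change in volume, while the analysis refers to change in atrophy, which is already a change.

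**Working it through.** The protocol gives no figure to reproduce here. The check has three parts.

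**1. Scans taken against time points analysed (Core Study)**

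| Measure | 6 mo (V14) | 12 mo (V16) | 18 mo (V18) | 21 mo (V20, off drug) |
|---|---|---|---|---|
| Scan scheduled | yes | yes | yes | yes |
| Left and right hippocampus, whole brain, ventricles | listed | listed | listed | no |
| Total hippocampus | **no** | listed | listed | no |

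The total uses 2 of the 4 scheduled post-baseline scans and the other volumes use 3. I take total to be left plus right, which the protocol does not state in terms.

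**2. Dose switch**

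Re-assignment happens at a scheduled visit (section 9.1), and scans fall in the 7 days before the visit. A 5 or 15 mg subject re-assigned at Visit 14 or 15 thus has the 6-month scan on the randomised dose and the 12- and 18-month scans on 50 mg. The documents do not say how many subjects this concerns.

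**3. Precision of the 18-month arm mean**

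Input from the protocol: n = 15 per arm (section 9.7.2). Assumptions, because the protocol gives none: unit variance, constant correlation ρ between visits, fraction d1 lost between 6 and 12 months, a further d2 lost between 12 and 18 months, covariance known, and no early-discontinuation scan. Put n2 = n(1 − d1) and n3 = n(1 − d1 − d2).

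- Visits 12 and 18 only: V = (1 − ρ²)/n3 + ρ²/n2.
- Visits 6, 12 and 18: V = s/n3 + β²[1/n + (1 − ρ²)/n2 + ρ²/n + 2ρ/n], with β = ρ/(1 + ρ) and s = 1 − 2ρ²/(1 + ρ).

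No dropout: both reduce to 1/15 = 0.0667, so nothing is lost.

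High end (ρ = 0.9, d1 = 0.30, d2 = 0.10, so n2 = 10.5 and n3 = 9):

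- 12 and 18 only: 0.19/9 + 0.81/10.5 = 0.0983.
- With 6 months: 0.1474/9 + 0.2244 × (0.0667 + 0.0181 + 0.0540 + 0.1200) = 0.0164 + 0.0581 = 0.0744.
- SE ratio: √(0.0983/0.0744) = 1.149.

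Low end (ρ = 0.5, d1 = d2 = 0.05, so n2 = 14.25 and n3 = 13.5):

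- 12 and 18 only: 0.75/13.5 + 0.25/14.25 = 0.0731.
- With 6 months: 0.6667/13.5 + 0.1111 × 0.2026 = 0.0719.
- SE ratio: 1.008.

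SE without the 6-month scan divided by SE with it:

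| d1, d2 | ρ = 0.5 | ρ = 0.7 | ρ = 0.9 |
|---|---|---|---|
| 0.05, 0.05 | 1.008 | 1.015 | 1.022 |
| 0.10, 0.10 | 1.017 | 1.029 | 1.045 |
| 0.20, 0.10 | 1.029 | 1.056 | 1.093 |
| 0.30, 0.10 | 1.042 | 1.084 | 1.149 |

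The subjects with only a 6-month scan number 15 × 0.05 ≈ 0.8 to 15 × 0.30 = 4.5 per arm.

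**The case against.** The best defence is that section 9.7.1.6.3 names the time points to be reported, not the rows of the model. It lists t-tau and p-tau at 18 months only, while section 9.7.1.7.2 analyses them from 4 weeks up to 18 months. The SAP, not shown, may put the 6-month visit in the model and report 12 and 18 months. That possibility stands, but it does not explain why one list gives left and right hippocampus a 6-month time point and their total none.

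Some other defences hold. Many subjects who stop after Visit 14 will have an early-discontinuation scan, which the calculation ignores, so the true loss may be smaller. Section 9.7.1 promises further analyses of re-assigned subjects. No efficacy endpoint is primary, and 15 per group has no stated power basis.

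A reader might also infer that the 6-month data are thrown away. They are not: they are analysed as left and right volumes. Nor is the Visit 20 scan unused. Under Appendix 6 and Table 14 footnote f it serves as the Visit 21 result and extension baseline, from which change in every volume, total hippocampus included, is summarised. It is off drug, so omitting it from a Core Study model loses no on-dose data. Wanting it as a Core time point is a preference.

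**Conclusion.** The inconsistency is real, unexplained and repeated in the objective, the endpoint and the analysis. Its cost is small: none for the 18-month arm mean if nobody drops out, otherwise a standard error about 1% to 15% larger without the 6-month scan. Put the other way, adding the scan lowers it by about 1% to 13% (1 − 1/1.149 = 0.13). These figures rest on assumed correlations and dropout, and ignore early-discontinuation scans. In addition, an unknown number of re-assigned subjects lose their only scheduled on-treatment scan at the randomised dose for this endpoint.

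It would be tempting to conclude that the comparison with placebo is biased. The documents do not support that: they give no dropout rate or pattern, and a shift in one arm's mean would largely cancel in the difference if dropout and decline were similar across arms. For an exploratory endpoint the severity is minor.

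**What to change.** In section 8.3(c), section 9.7.1.1.3, section 9.7.1.6.3 and the synopsis, define the endpoint as change from baseline in total hippocampal volume at 6, 12 and 18 months. Replace atrophy with volume, and include all three visits in the MMRM as for the other volumes. If 6 months was left out on purpose, state why. This costs wording only, because the scans are already scheduled and each side is already measured at that visit.

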9.7.1.7 Pharmacokinetic, Pharmacodynamic, Pharmacogenomic, and Other Biomarker Analyses

9.7.1.7.1 PHARMACOKINETIC ANALYSES

The PK Analysis Set will be used for elenbecestat (E2609) concentration listings and for summaries of elenbecestat (E2609) concentrations in plasma and CSF by dose and day. elenbecestat (E2609) metabolite PK data may also be listed and summarized. (revised per Amendment 04)

A population PK approach will be used to characterize the plasma PK of elenbecestat (E2609). For this approach, plasma PK data from this study will be pooled with relevant data from Phase 1 studies. As appropriate, the effect of covariates on the PK of elenbecestat (E2609) will be evaluated. The PK model will be parameterized for oral clearance (CL/F) and apparent volume of distribution (V_z/F) for elenbecestat (E2609). Derived exposure parameters such as steady state area under the concentration time curve (AUC) and average concentration (C_{avg}) of elenbecestat (E2609) and other derived parameters will be calculated from the model using the individual estimates parameterized for oral clearance and dosing history. (revised per Amendment 04)

